Data analysis:	
In this study, both patients and eyes will be considered as the analysis unit. Baseline characteristics will be summarized using descriptive statistics. For continuous variables, the mean, standard deviation, median and range will be presented. For categorical variables frequency and proportion will be used. Variables are identified and calculated at the index diagnosis and throughout the follow-up period for primary outcomes like VA.
 
In the progression analysis, the population will be restricted to patients with a minimum follow-up time (i.e. multiple visits at least one year apart, at least two years), or patients with valid VA reading at the index diagnosis and a second follow-up timepoint. [REDACTED]
 
The analysis of incident and prevalent calculations will use as the denominator, all patients referred to the retinal specialist. The proportion of patients with a GA diagnosis referred to the retinal specialist will be put into perspective by comparing to other conditions, such as proportion of patients referred to the retinal specialist with a diabetic macular edema (DME) diagnosis, or with a diabetic retinopathy (DR) diagnosis etc. Additionally, extrapolations will be done to approximate to a population-based estimate.
									
Milestones:	
 
 Start of data collection	05/2023		
 
 End of data collection	06/2023		
 
 Final report of study results	06/2023		
 
	Start of data collection	05/2023		End of data collection	06/2023		Final report of study results	06/2023	
Start of data collection	05/2023									
End of data collection	06/2023									
Final report of study results	06/2023									

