8. RESEARCH QUESTION AND OBJECTIVES

Research Question

To quantify and describe patients with a GA diagnosis in at least one eye. [REDACTED]

Primary objectives

To describe the characteristics* of patients with GA in at least one eye.

To describe characteristics* of the study eye and the fellow eye, at index diagnosis

To evaluate and characterize the progression of newly diagnosed patients with GA during each year for 5-year follow-up period. In particular, to describe patients' characteristics, study eye and the fellow eye characteristics over the 5-years follow up. [REDACTED]

Secondary objectives

To determine the first time occurrence of GA in the study eye, during the study period.

To determine the proportion of patients with GA in the study eye, over the study period.

To compare the GA first time occurrence and the proportion of GA, relative to other retinal conditions, and relative to proportion of retinal specialist contributing to [REDACTED] and the overall US retinal specialist.

To evaluate patients' management (i.e. patients visits and procedures) over the study period.

To describe [REDACTED]

the overall GA population.

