For all time to event metrics, mean (SD), median and range will be summarized, while proportions will be summarized using N (%).

Kaplan Meier or Cox Hazard ratios may be applied when analyzing disease progression. Additionally, it will be determined how patients progress during the 1,2,3,4,5 years follow up according to the lesion location, and lesion size.

Analysis for objective:

To determine the occurrence of GA in the study eye during the study period (at the 12 (24, 36, 48, 60) month follow up period).

The calculation of the occurrence (new cases) of GA will be tracked against the overall number of patients included in the retinal specialist database (████████ database) in a time period (year) as the denominator initially.

The analysis to calculate the prevalent cases will include all patients with a GA diagnosis active in the database in the given time period in the numerator, and all patients included in the retinal specialist database (████████ database) will be used as the denominator initially.

Since, this analysis is referring to a population attending a retinal specialist during a given time period and therefore is not a general population-based estimates, in order to give a context to the data, the proportion of other common diagnosis in patients over 50 years or older attending the clinic in the same time period (e.g. diabetic macular edema, diabetic retinopathy, proliferative diabetic retinopathy, and wAMD) will be calculated. The denominator will be all patients attending to the retina specialist in the given time period using the age group category that is applicable in this study (50 years or older).

For the initial calculations, the look back period in 2015 will be used to discard patients with prevalence GA diagnosis in the subsequent years. prior diagnosis will be excluded and only new cases diagnosis in the time period will be considered in the numerator when calculating incidence.

The calculations will be conducted by calendar year, and absolute numbers (n) and correspondent percentage (%) will be provided. As a sub analysis, it will be evaluated if changes occurred after the third quarter of 2021, corresponding with the ██████████

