Subgroups will be compared against one another to identify any differences in populations leading to progression. The characteristics will be extracted at the time of assignation to the group i.e. patient do not [REDACTED] in year one is contributing with his characteristics extracted at year 1 to the group (no progressors), that patient [REDACTED] at year 5 is contributing with his characteristics extracted at year 5 to the progressor group.

Summary will include descriptive statistics; continuous variables will be described by absolute numbers, the mean (SD), median and range, while categorical variables will be described using frequency and proportion. For discrete demographics or clinical characteristics, chi-squared test of proportion will be done to assess meaningful difference (standardized mean difference SMD may be used as an alternative), while continuous variables will be analyzed using SMD. Following univariate analysis on each metric, a multivariate logistic regression model will be run including relevant metrics identified in the univariate analysis.

Additional information on the analysis is described below:**Patient Demographics (at index and follow up):**

BOEHRINGER INGELHEIM Group of Companies**NIS Protocol Template****Page 25 of 30****Study number: 1484.0014****Document number: <insert>**

N (%); Age, gender, region; Bilateral status, other eye related diagnosis in study and fellow eye; Distribution by months of follow up; Concomitant illnesses (diabetes, cataract, etc.); Lesion location and size (along with % capture rate)

Progression : Progression of GA over time; Fellow eye AMD status; [REDACTED] (study and fellow eye) Mean (median/IQR) time to conversion; Conversion to GA (fellow eye) Mean (median/IQR) time to conversion; Proportion of patients with wAMD and GA (N, %)

[figure not shown]
Treatment Characteristics (follow up): Number of visits over time; Number of treatments over time, Mean (median) time to study treatment; Type of treatment – Anti-VEGF, Laser, Combination, Mean (median) time on therapy

New cases occurrence and prevalent cases of GA (stratified by index year): N (%)

- Age, gender
- Distribution by months of follow up
- Calculation to the % of patients attending the retinal specialist over the same time period for other retinal conditions i.e. wAMD, DR, dry AMD or DME.

Visual Acuity Outcomes

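### The comparison of first-time GA occurrence with other retinal diseases has no comparator figure, and the GA new-case denominator keeps patients who already have GA

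*Combined protocol and SAP*

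**What the plan says.** The secondary objective in section 8 reads "To compare the GA first time occurrence and the proportion of GA, relative to other retinal conditions". It names two comparisons.

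Section 9.7.1 gives GA two figures per calendar year: new cases and active cases, each as n and %. For DME, DR, proliferative DR (PDR) and wAMD it gives one, "the proportion of other common diagnosis in patients over 50 years or older attending the clinic in the same time period". The output list later in section 9.7.1, which adds dry AMD, repeats this as "Calculation to the % of patients attending the retinal specialist over the same time period for other retinal conditions".

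On the GA new-case denominator, section 9.7.1 says: "The calculation of the occurrence (new cases) of GA will be tracked against the overall number of patients included in the retinal specialist database". The abstract (section 4, data analysis) agrees: "The analysis of incident and prevalent calculations will use as the denominator, all patients referred to the retinal specialist". Earlier diagnoses are dealt with on the other side of the fraction: "only new cases diagnosis in the time period will be considered in the numerator when calculating incidence". On the look-back, the plan says that "the look back period in 2015 will be used to discard patients with prevalence GA diagnosis in the subsequent years".

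The limit of 50 years or older is written into the comparator denominator. It is not stated for the GA denominators.

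**The concern.** The objective asks whether GA is first diagnosed more or less often than other retinal diseases. That needs a new-case figure for each disease, built by one rule. The plan has one for GA only, so half of the objective cannot be answered as written. The output list also places the comparator percentages under the heading for new and prevalent GA, where a reader could set unlike measures side by side.

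The second issue is smaller. A patient already coded with GA cannot become a first-time case, yet still counts in the denominator, which pulls the new-case percentage down. An age limit that applies to the comparators and perhaps not to GA would pull it down further.

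**Working it through.** The documents state no incidence or proportion for this objective, so there is no figure to reproduce. The check sets the sections side by side and then sizes the effect from the feasibility counts.

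**1. What exists for each disease**

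| Disease | All-cases % planned (9.7.1) | New-case % planned (9.7.1) | Incident visit defined (9.3.3.1) |
|---|---|---|---|
| GA | yes | yes | yes |
| wAMD | yes | no | yes |
| Dry AMD | yes (output list) | no | yes |
| DME, DR | yes | no | no |
| PDR | yes | no | no |

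Section 9.9 also says that newly diagnosed wAMD will be identified, but section 9.7.1 does not use this in the comparison.

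**2. Whether the look-back repairs the denominator**

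Table 1 gives GA no ICD-9 code. Section 9.1.1 uses January to September 2015 to find dry AMD by ICD-9, and ICD-10 began in October 2015. So 2015 can reveal GA codes in its last quarter at most. Patients first coded with GA in 2016 or later stay in the denominators of all following years.

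**3. Inputs**

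- Section 9.5: 72,718 GA patients from 2016 onward, with 22 months' average follow-up.
- January 2016 to April 2023: 88 months, or 7.33 years.
- Section 9.9: 1.6 million eyes seen in 2022. Assuming two eyes per patient, 1,600,000 / 2 = 800,000 patients.
- Assumed: even accrual of new cases, 2022 as a typical year, and 60–100% of patients aged 50 or older, so D = 480,000 to 800,000.

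**4. New and prior GA patients**

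- New per year: 72,718 / 7.33 ≈ 9,916.
- Under follow-up at one time: 72,718 × 22/88 ≈ 18,180.
- Cautious higher value for prior GA among a year's attendees: 18,180 + 9,916 = 28,096.

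**5. Denominator effect: factor = D / (D − prior GA)**

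| D | Prior GA | New / D | New / (D − prior) | Factor |
|---|---|---|---|---|
| 800,000 | 18,180 | 1.24% | 1.27% | 1.023 |
| 800,000 | 28,096 | 1.24% | 1.28% | 1.036 |
| 640,000 | 18,180 | 1.55% | 1.59% | 1.029 |
| 640,000 | 28,096 | 1.55% | 1.62% | 1.046 |
| 480,000 | 18,180 | 2.07% | 2.15% | 1.039 |
| 480,000 | 28,096 | 2.07% | 2.19% | 1.062 |

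In the extreme case where every other GA patient counts as prior GA (72,718 − 9,916 = 62,802), the factor is 1.085 to 1.151.

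**6. Difference between the two kinds of measure, for GA itself: (prior + new) / new**

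- (18,180 + 9,916) / 9,916 = 2.83
- (28,096 + 9,916) / 9,916 = 3.83

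**7. Age limit**

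If the limit applies to the comparators and not to GA, and 60–90% of patients are aged 50 or older (assumed), GA percentages are too low by a factor of 1/0.9 = 1.1 to 1/0.6 = 1.7.

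**The case against.** The strongest reply is that the plan's real comparison is sound. The abstract puts the proportion with GA beside the proportion with DME or DR, and section 9.7.1 offers the comparator figures as context for a clinic-based population. That stands. In kind of measure, the proportion comparison is like for like.

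A reader might infer that new GA will be divided by, or ranked against, total DME or wAMD. No section plans that ratio, so the 2.8-fold figure describes a possible misreading of the tables and not a planned result. A reader might also carry the denominator effect over to wAMD and dry AMD, where existing cases are a larger share of attendees. No comparator new-case figure is planned, so that error is not in the plan.

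On the denominator, new diagnoses per attendee is a legitimate measure of caseload. The plan also calls the denominator an initial one and speaks of discarding prevalent GA. These words leave room but do not settle the matter. No at-risk denominator is defined anywhere, and the explicit exclusion names only the numerator.

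The feasibility counts also used exam notes, whereas planned incidence uses ICD-10 codes, and the arithmetic treats every counted patient as new since 2016. The sizes are therefore orders of magnitude. The codes appendix was not available and may hold comparator code lists, but the analysis text calls for no comparator new-case count.

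**Conclusion.** The concern holds in a limited form. The objective names a first-occurrence comparison, and the analysis section supplies no comparator figure for it. Incident-visit definitions exist for dry AMD and wAMD but are not used here, and none is given for DME, DR or PDR. The proportion half of the objective is covered.

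Keeping prior GA in the new-case denominator understates first-time occurrence by about 2–6% in relative terms under the assumptions listed. This is small, and the missing comparator figure matters more. The age limit needs one clear statement, because its possible effect is larger than that of the prior cases. The documents do not show that GA will be reported as severalfold rarer than its comparators. The change is worth making before outputs are run.

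**What to change.** **Preferred.** For GA and each comparator, count first-coded cases per calendar year among attendees aged 50 or older with no earlier code for that disease. Use one common ICD-10 look-back window for all diseases, because Table 1 gives wAMD an ICD-9 code and GA none. State that the window is short in the early years. Compare new with new and total with total, in separate output blocks.

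**Alternative.** Restrict the between-disease comparison to proportions and amend the section 8 objective accordingly. Still remove prior GA from the GA new-case denominator, and apply the limit of 50 years or older to it.

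**Cost.** The preferred route needs additional code lists and queries on the static dataset described in section 9.6, and no new data. Its downside is that some comparator cases counted as new in the early years will be old cases not seen in the window. The alternative costs a wording change and one corrected denominator, and gives up the first-occurrence comparison.

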Population:	
Patients attending a retina specialist, contributing to the [REDACTED] Database. Patients will be identified in the database from January 1, 2015, to April 30, 2023.
 
From those, our study population will be patients ≥ 50 years with a GA diagnosis in at least one eye will be eligible for this study.
 
The study period was selected to be able to identify patients with GA using the ICD-10 codes introduced in that year. The period from January 2015 until October 1st, 2015 will be used to identify patients diagnosed with ICD-9 codes and further classify them as new cases or patients with an previous diagnoses.
		
Variables:	
A primary outcome variable is visual acuity (VA), reported using converted Early Treatment Diabetic Retinopathy Study (ETDRS) letters.
 
[REDACTED]
 
[REDACTED]
 
[REDACTED]
 
Demographic characteristics – including age, gender, patient history, visit history
 
Clinical Characteristics – including ocular comorbidities, lens status, systemic conditions
		
Data sources:	
The [REDACTED] database consists of de-identified Electronic Health Records from a geographically diverse panel of 360+ United States based private retinal specialists contributing data from 70+ practices. Over the datasets entire history, there have been about 2 million patients and about 13 million patient visits.
		

BOEHRINGER INGELHEIM Group of Companies

NIS Protocol Template

Page 9 of 30

Study number: 1484.0014

Document number: <insert>

Study size:	
All patients available in the database and meeting the study criteria will be included.
 
The [REDACTED] includes approximately 400,000 patient eyes diagnosed with dry AMD, and around 70,000 patients diagnosed with GA during the study period. After the initial feasibility analysis, it is expected, given the study criteria, that there will be around 100,000 eyes included. However, this number might change in the final analysis.
									

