9. RESEARCH METHODS

9.1 STUDY DESIGN

This is an observational cohort study based on existing data.

BOEHRINGER INGELHEIM Group of Companies**NIS Protocol Template****Study number: 1484.0014****Page 12 of 30****Document number: <insert>****9.1.1 Study population**

Study inclusion criteria: All patients ≥ 50 years, with a GA diagnosis in at least one eye, including in the [REDACTED] database identified during the study period (January 2015 to April 2023).

Exclusion criteria: Patients without the information of laterality will be excluded.

No other exclusion criteria are applied for the identification of the study population and description of the patients and eye at baseline.

Additional note:

For certain analysis the patient population will be restricted to those with at least 12, 24, 36, 48, or 60 months of history following diagnosis of GA. For the analysis requiring a VA reading, a restriction to those patients with valid VA readings at the index diagnosis and the respective follow-up times will be applied.

For analysis estimating the size of the GA population relative to other retinal diseases, the same timeframe requirements that the study population will be applied. In this population, any patient in the database will be eligible, and the diagnosis of DME, DR or other conditions may be used for subgroup comparisons.

Primary Disease Definitions

In the [REDACTED] Database, retinal and other diseases are identified using the International Classification of Diseases (ICD), Tenth Revision, Clinical Modification. ICD 10 codes were launched in the USA in October 2015, and are the only version of ICD codes with adequate descriptions of GA and dry AMD severity. As such, only ICD 10 codes will be analyzed in this study and the study period defined above is directly related to the launch of ICD 10 plus a small buffer allowing for physician familiarity.

These codes are entered by the physician at patient visit, with an associated laterality. This, along with the ICD 10 laterality is used in combination to confirm in which eye the disease is occurring. For this study, a patient eye will be considered to have the study disease so long as there is an accompanying ICD code. The primary study diseases to be analyzed are dry AMD, GA and wAMD, and will be identified using the ICD codes in Table 1 below.

Table 1. Study disease definitions-codes.

Study Disease Definitions			
	Dry AMD*	Dry AMD with GA*	wAMD*

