ICD 10	H35.311X, H35.312X, H35.313X, H35.319X	H35.3113, H35.3114, H35.3123, H35.3124, H35.3133, H35.3134, H35.3193, H35.3194	H35.321X, H35.322X, H35.323X, H35.329X
ICD 9 (2015 only)	362.51	N/A	362.52

*a comprehensive list of all AMD ICD codes is included in the Appendix

BOEHRINGER INGELHEIM Group of Companies**NIS Protocol Template****Study number: 1484.0014****Page 13 of 30****Document number: <insert>**

Patients could have simultaneously a diagnosis of wAMD and GA in the same eye. If both conditions are present, wAMD will be described as part of the comorbidities of the study or fellow eye. Patients could also have other ocular comorbidities affecting VA (section 9.3.3), those will be described and for the progression analysis will be analyzed separately.

For the follow-up analysis in the study eye or fellow eye, results will be described for all GA patients, patients with GA and wAMD, and patients with patients with GA only (without wAMD or other ocular comorbidities).

As the progression analysis tracking multiple different metrics across 2 eyes, it will be conducted at the patient level. Bilateral AMD disease is quite common (and will be identified), therefore the following methodology will be used to identify the 'Study' (primary) eye and the 'Fellow' (secondary) eye:

Study Eye – The first study eye in patient history identified with GA in the [REDACTED] database. GA is the only identifying disease in this case, and wAMD or dry AMD (without GA) in the study eye is not taken into account for study eye definition. If patients are bilaterally diagnosed, the study eye will be selected at random.

Fellow Eye – is defined as the other eye in a patient having their study eye diagnosed with GA. The fellow eye can have dry AMD, wAMD, GA or other retinal conditions. The fellow eye will be followed for progression purposes throughout the study.

Disease Status

Patient eyes will be identified at every visit throughout the study period to estimate the first time occurrence of GA and to estimate the proportion of patient with the disease over the years of the study period. Each visit will be classified as either an incident or a prevalent visit, defined below:

Incident visit – The first visit in patient eye history identified with GA in the [REDACTED] database. This timepoint also acts as each patients' index diagnosis. The incident visit may only occur once and contribute to one calendar year.

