Prevalent visit – all visits following the incident visit in patient eye history while identified with GA in the [REDACTED] database. Prevalent visits may occur year after year throughout the patients' journey.

Study period

Patients will be identified from January, 2015 to April, 2023.

Selection period: Eligible patients must have at least one GA diagnosis between October 2015 and April 2023. The date of the first GA diagnosis will be considered as index date. For all follow up analysis, eligible patient eyes should be divided in those with at least 12, 24, 36, 48 and 60+ months of follow up. follow up requires multiple visits spanning over the outlined durations and total follow up is defined as the time between incident diagnosis and the final visit in the dataset.

BOEHRINGER INGELHEIM Group of Companies**NIS Protocol Template****Page 14 of 30****Study number: 1484.0014****Document number: <insert>**

Follow-up period: up to 60-month period following the index diagnosis date of GA (exploratory follow-up of 1, 2, 3, 4, 5 years may be run as cutoff points)

Pre-selection period: January 2015-September 2015. This period will be used to identify patients who have dry AMD using ICD9 coding, and will help to assign patients into the incidence or prevalence status.

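### As written, the 2015 look-back cannot identify existing GA, so early incidence and the newly diagnosed progression cohort may be misclassified

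*Combined protocol and SAP*

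**What the plan says.** Section 9.7.1, on the occurrence of GA, states that "the look back period in 2015 will be used to discard patients with prevalence GA diagnosis in the subsequent years", and that only new cases enter the incidence numerator. Three other places describe the same period:

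- The Abstract (section 4, Population) says the months of 2015 before October "will be used to identify patients diagnosed with ICD-9 codes and further classify them as new cases" or as previously diagnosed.
- Section 9.1.1, Study period, gives January to September 2015 as the pre-selection period: "This period will be used to identify patients who have dry AMD using ICD9 coding". It adds that this will help to assign incidence or prevalence status.
- Section 9.1.1, Primary Disease Definitions, says "only ICD 10 codes will be analyzed in this study" and explains the study period by the ICD-10 launch "plus a small buffer allowing for physician familiarity".

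The ICD-9 row of Table 1 lists 362.51 for dry AMD, 362.52 for wAMD and N/A for GA. Section 9.3.2.1 bases GA incidence and prevalence on ICD-10 codes.

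The incident visit, which is also the index, is "The first visit in patient eye history identified with GA in the" database (section 9.1.1, Disease Status). Selection opens in October 2015: "Eligible patients must have at least one GA diagnosis between October 2015 and April 2023". No GA-free observation is required before index.

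**The concern.** A look-back removes prevalent disease only if that disease can be recorded in the look-back window. Here it cannot, because ICD-9 does not separate GA from other dry AMD. The plan does not say what happens, for GA status, to a patient coded 362.51 in 2015. Two analysts could therefore report different incidence from the same data:

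- **362.51 not used.** GA already managed in a contributing practice becomes incident at its first ICD-10 GA code, so incidence in the first ICD-10 years may be too high.
- **362.51 used to discard patients.** Patients with dry AMD who truly develop GA later leave the incidence numerator, so some true new GA is not counted.

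The problem reaches a primary objective. Sections 8 and 9.7.1 follow newly diagnosed GA for 5 years, and section 9.2.1 plans a subgroup comparison of newly diagnosed against existing GA. The exclusion in 9.7.1 is tied to the incidence numerator, so the progression cohort starts at the first GA code under either reading. Its time zero may mix new disease with disease that is already advanced.

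The baseline description of all GA patients does not depend on the look-back. Nor does the US extrapolation, which uses all prevalent GA.

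**Working it through.** **Can the look-back see GA?** The plan gives no numerical result to reproduce, so the first step is to set its definitions side by side.

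| Element | Source | Content |
|---|---|---|
| Task | 9.7.1 | Remove existing GA |
| Window | 9.1.1, Study period | January to September 2015 (9 months) |
| ICD-10 launch | 9.1.1, Primary Disease Definitions | October 2015 |
| ICD-9 code for GA | Table 1 | N/A |
| Basis of disease status | 9.1.1 and 9.3.2.1 | ICD code; for GA, ICD-10 |

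Months in the window with a usable GA code: 0 of 9.

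**Does another part of the plan fill the gap?**

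- October to December 2015 has ICD-10 codes, but it is selection time. A first GA code there sets the index. The buffer mentioned in 9.1.1 is never turned into a washout.
- Exam notes were used for the feasibility count in section 9.5 (period from 2016). They are not assigned to the look-back.
- Stratifying by index year (9.7.1) would show an early excess but not correct it.
- Section 9.9 discloses earlier diagnosis by other providers. It does not disclose that existing GA in the same practices is invisible before ICD-10.

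**Which results are exposed?** Index months run from October 2015 to April 2023: 3 + 84 + 4 = 91. With data ending in April 2023, the latest index that can reach *m* months is *m* months earlier. The last two columns apply an example run-in from October 2015 to December 2016 (3 + 12 = 15 months).

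| Follow-up (months) | Latest index | Index months available | Left after run-in | Reduction |
|---|---|---|---|---|
| 12 | April 2022 | 79 | 64 | 15/79 = 19.0% |
| 24 | April 2021 | 67 | 52 | 15/67 = 22.4% |
| 36 | April 2020 | 55 | 40 | 15/55 = 27.3% |
| 48 | April 2019 | 43 | 28 | 15/43 = 34.9% |
| 60 | April 2018 | 31 | 16 | 15/31 = 48.4% |

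How long an early excess would last is unknown, so three assumed cuts are shown.

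| Early period to | Months | Share of 60-month window | Share of 12-month window |
|---|---|---|---|
| December 2015 | 3 | 3/31 = 9.7% | 3/79 = 3.8% |
| June 2016 | 9 | 9/31 = 29.0% | 9/79 = 11.4% |
| December 2016 | 15 | 15/31 = 48.4% | 15/79 = 19.0% |

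These are shares of calendar months, not of patients, and they do not estimate bias.

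**What would other run-ins leave?** Requiring an ICD-10-era visit 12 months before index moves the earliest index to October 2016. The 60-month window is then 3 + 12 + 4 = 19 months, a loss of 12/31 = 38.7%. A run-in to June 2017 leaves July 2017 to April 2018, which is 10 months, a loss of 21/31 = 67.7%.

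**The case against.** The strongest reply is that 9.7.1 refers to a look-back in 2015 without limiting it to January to September. October to December 2015 carries ICD-10 GA codes and could remove some existing GA from 2016 onwards. The text does not support this as a rule. The Abstract and 9.1.1 tie the classification window to ICD-9, and 9.1.1 makes those three months eligible for index. On the generous reading, the look-back would still be only three months long.

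Other points:

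- **ICD-9 has a proper use.** Section 9.3.3.1 defines incident and prevalent visits for dry AMD and wAMD as well, and 362.51 and 362.52 serve those. This stands, but that section gives no rule for classing 362.51 patients with respect to GA.
- **Earlier diagnosis is disclosed.** Section 9.9 partly acknowledges a mixed time zero, but only for diagnosis elsewhere.
- **Yearly prevalent counts are also affected.** Section 9.3.2.1 counts as prevalent those diagnosed in past years, so calling existing GA incident shifts the early prevalent counts too. This stands. It does not reach the extrapolation, which 9.7.1 bases on all active GA.
- **The 31-month count is strict.** The 60-day VA buffer would admit index dates to about the end of June 2018, roughly 33 months, and 15/33 is still 45%. Kaplan-Meier estimates use later index dates for the earlier intervals. Both points are fair. Under the definition of follow-up in 9.1.1 (index to final visit), 31 is correct.
- **The remedy is heavy for a descriptive study.** Wording, a monthly table and a disclosure would resolve the contradiction itself. They would not show whether the progression results depend on it.

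The codes appendix (Annex 1) is a separate file that I have not seen. If it or the 2015 notes identify GA, the protocol should say so.

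**Conclusion.** The concern holds. The rule in 9.7.1 cannot be carried out with the codes and dates that the plan gives. This is a contradiction in the text, not a missing detail. Incidence in the first ICD-10 years may be too high if 362.51 is ignored, and it omits some true new GA if 362.51 is used. Under both readings the newly diagnosed cohort may include existing GA.

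The documents do not allow the bias to be sized, and none is claimed. What can be counted is exposure: all results requiring a full 60 months come from the first 31 of 91 index months. Under the assumed cuts, the early period makes up 10% to 48% of those 31 months, against 4% to 19% of the 79 that can reach 12 months. Confidence in the contradiction is high. It rests on Table 1 and the protocol text. The point should be fixed before the data are analysed.

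**What to change.** 1. Reconcile the Abstract, 9.1.1 and 9.7.1 with Table 1. State that 362.51 alone does not set GA incident or prevalent status, and whether eyes coded 362.51 in 2015 enter the dry-AMD-to-GA conversion analysis in 9.7.1.
2. Tabulate first GA codes by month from October 2015. Treat an initial ICD-10 period as run-in, for example to December 2016, confirmed or changed from that table. Report its cases as first recorded GA with onset unknown.
3. Start main incidence after the run-in, counting all first GA codes.
4. Keep the full first-recorded-GA cohort as the main progression analysis. Add a sensitivity analysis in patients indexed after the run-in who have an ICD-10-era visit at least 12 months before index and no earlier GA code. Apply the same washout to numerator and denominator for a sensitivity estimate of incidence.
5. If feasibility shows that 2015 exam notes identify GA, name them as an added look-back source.
6. Add the coding gap to section 9.9.

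The work is protocol wording, one monthly table, one extraction filter and one set of sensitivity tables. The downsides should be stated:

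- With a run-in to December 2016 there is no interpretable incidence for 2015-2016, and the 60-month window in the sensitivity cohort falls from 31 to 16 months. A shorter run-in gains little, because the prior-visit rule alone leaves 19.
- The washout drops genuine new referrals, which is why the full cohort stays the main analysis.
- Existing GA coded as other dry AMD at the earlier visit may remain.
- The size of the sensitivity cohort is unknown. Section 9.5 shows only 20,503 of 72,718 patients (28%) with visits after 3 years, so it should be counted in feasibility first.
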